8 STATISTICAL PLAN

8.1 Sample Size

The sample size is driven by interest in the IOP lowering effect of H-1337. The study is designed to test whether one or more concentrations of H-1337 are superior to the vehicle control in the reduction of IOP. With $n = 20/\text{group}$ this stage is powered at 94% to detect a difference in IOP reduction of 4.0 mmHg between groups against a standard deviation of 3.5 mmHg (2-sided t-test, alpha=0.05).

Adverse events: With 20 subjects per group there is a 95% certainty that an event that is not observed would have a true incidence rate of no more than 15%.

Hyperemia: Scored on a 5-point scale from 0 to 3. Assume the SD is 20% of the scale range or 1 unit. Then, with $n = 20/\text{group}$ there is 86% power to detect a mean difference of 1 unit between pairs of groups (2 group two-sided t-test, alpha=0.05). If a response is defined as a hyperemia score ≥ 3 and the response rate in the control group is 10%, then with $n = 20/\text{group}$ there is 85% power to detect a difference in response rates of 46% (Fisher's exact test).

In general, with 20 subjects per group there is 86% power to detect an effect size of 1.0.

If a concentration is chosen that is less than the maximum, the safety data from the higher doses can be combined to increase power.

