Moderate (+2) =	General swelling
Severe (+3) =	Extensive swelling of the eyelid(s), with or without eversion of upper and/or lower lids.

CONJUNCTIVA

Hyperemia

None (0) =	Normal: few vessels of bulbar conjunctiva easily observed
Minimal (+0.5) =	Trace flush, reddish-pink color of the bulbar conjunctival
Mild (+1) =	Mild flush – reddish pink of the bulbar conjunctiva
Moderate (+2) =	Moderate, bright reddening of the bulbar conjunctiva
Severe (+3) =	Deep, severe, bright and diffuse reddening of the bulbar conjunctiva

CONJUNCTIVA (continued)

Edema

None (0) =	Normal, no swelling of the conjunctiva or less than mild
Mild (+1) =	Slight diffuse or regional swelling of the conjunctiva
Moderate (+2) =	General swelling of the conjunctiva
Severe (+3) =	Extensive swelling of the conjunctiva

CORNEA

Edema

None (0) =	Transparent and clear or less than mild
Mild (+1) =	Dull glassy appearance
Moderate (+2) =	Dull glassy appearance of epithelium with large number of vacuoles
Severe (+3) =	Epithelial bullae and/or stromal edema, localized or diffuse, with or without stromal striae

ANTERIOR CHAMBER

Cells

None (0) =	No cells seen or less than mild
Mild (+1) =	1-5 cells
Moderate (+2) =	6-10 cells
Severe (+3) =	11-20 cells
Hypopyon (+4) =	> 20 cells, Hypopyon Formation (indicate size of hypopyon)

Flare

None (0) =	No Tyndall effect or less than mild
Mild (+1) =	Tyndall beam in the anterior chamber has a mild intensity
Moderate (+2) =	Tyndall beam in the anterior chamber is of strong intensity
Severe (+3) =	Tyndall beam is very intense. The aqueous has a white, milky appearance

LENS

Phakic	Yes/No for each eye
Aphakic	Yes/No for each eye
Pseudophakic	Yes/No for each eye

Lens Opacity (for phakic only)

None (0) =	None present or less than mild
Mild (+1) =	Subtle
Moderate (+2) =	Moderate
Severe (+3) =	Dense

Pupillary Diameter: Measurement of pupil size should occur under normal lighting conditions to the nearest 0.5 mm using a millimeter ruler or pupillary gauge while the patient fixates on a distant, non-accommodative target.

Conjunctival Hyperemia: Hyperemia will be assessed and recorded separately from biomicroscopy through direct visual observation prior to fluorescein instillation and IOP measurement. The hyperemia will be graded on a 0 to 3 scale using the photographic reference scale provided by the Sponsor for use in this protocol.

- 0 Normal: few vessels of bulbar conjunctiva easily observed
- 0.5 Trace flush, reddish-pink color of the bulbar conjunctival

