7.4 Intraocular pressure

The comparisons among treatment groups in IOP will be done for the various endpoints and time points. The outline of the analyses and groups is presented in Appendix 2.

For each visit in which IOP is measured descriptive statistics at each time point will be presented for the observed, change from baseline and % change from baseline values. In addition, at visits where five assessments are made descriptive statistics will be presented for the average of the observed values and the change from baseline and percent change from baseline where the values will be computed using average of five corresponding values at Day 0 as a baseline.

Descriptive statistics of IOP measures described above will be presented for the study eye, non-study eye and average of both eyes by time point and treatment group.

The 95% confidence intervals of the mean IOP by treatment group and time point and for diurnal IOP as well as for corresponding change from baseline will be presented.

For the IOP, diurnal IOP, and their change from baseline, each of the active treatment groups will be compared to the placebo group using the analysis of covariance (ANCOVA) model, separately for each time point. Baseline value will be used as a covariate. The difference between treatment groups in adjusted least-square means will be presented. Mean diurnal IOP will be presented as the mean of all values (including the 8 pm IOP value) (12-hour diurnal) and mean of all values up to the 4 pm IOP value (8 hour diurnal). If a subject is missing any time point for the calculation of the diurnal IOP, that subject will be excluded from the affected diurnal IOP analysis in the per protocol population.

The proportion of subjects reaching a target IOP (≤ 18 mmHg) at each time point and with the mean diurnal IOP for each visit will be presented by treatment group.

Within each dose level the change from baseline IOP will also be compared (a within subject comparison) with descriptive statistics.

Exploratory summaries may be presented to examine if treatment effects differ depending on iris color, age and baseline IOP.

Each comparison will be tested at the significance level of 0.05. No adjustments for multiple comparisons will be made.

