7.13 Ocular Hyperemia, Biomicroscopy, Ophthalmoscopy and Ocular Symptoms

The observations of ocular hyperemia, biomicroscopy, ophthalmoscopy, and ocular symptoms will be summarized in frequency tables based on the ordinal scales for each measure for each eye by time point and treatment group. In addition, the photographic assessment of ocular hyperemia will be summarized by descriptive statistics (See Appendix 2).

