9.2 Appendix 2. Efficacy Endpoints and Time Points

IOP

Category	Day 0 Visit	Day 1 Visit*	Day 4 Visit*	Days 14 & 28 Visits
Eye subgroups	Study eye Mean of both eyes	Study eye	Study eye	Study eye Mean of both eyes
Analysis variables	IOP & Diurnal IOP	
• IOP• Change in IOP from baseline (Day 0 Visit)*• % change in IOP from baseline (Day 0 Visit)*• Proportion of subjects achieving IOP \leq 18 mmHg	
• IOP• Change in IOP from baseline (Day 0 Visit)• % change in IOP from baseline (Day 0 Visit)• Proportion of subjects achieving IOP \leq 18 mmHg	
• IOP & Diurnal IOP• Change in IOP & Diurnal IOP (Day 0 Visit)• % change in IOP & Diurnal IOP (Day 0 Visit)• Proportion of subjects achieving IOP/Diurnal IOP \leq 18 mmHg
Analysis Time points	
• T_0$T_0 + 1$ hrs$T_0 + 2$ hrs$T_0 + 4$ hrs$T_0 + 8$ hrs$T_0 + 12$ hrs• Diurnal (mean of 5 measurements & mean of 4 measurements excluding $T_0 + 12$ hrs)	T_0	T_0	
• T_0$T_0 + 1$ hrs$T_0 + 2$ hrs$T_0 + 4$ hrs$T_0 + 8$ hrs$T_0 + 12$ hrs• Diurnal (mean of 5 measurements & mean of 4 measurements excluding $T_0 + 12$ hrs)
Treatment Groups/ Comparisons	H-1337 vs. Vehicle	H-1337 vs. Vehicle	H-1337 vs. Vehicle	H-1337 vs. Vehicle

*Note: the non-study eye will not be treated until after T_0 on the Day 4 visit. Day 0 measures will be used as baseline for all time points for the non-study eye.

Conjunctival Hyperemia by Photographic Assessment

Category	Day 0 Visit	Day 4 Visit*	Day 14 Visit	Days 28 Visit
Eye subgroups	Study eye Mean of both eyes	Study eye	Study eye	Study eye Mean of both eyes
Analysis variables	Conjunctival Hyperemia by Photographic Assessment	
HyperemiaChange in Hyperemia from baseline (Day 0 Visit)*	
HyperemiaChange in Hyperemia from baseline (Day 0 Visit)	
HyperemiaChange in Hyperemia from baseline (Day 0 Visit)
Analysis Time points	
Pre-T_0$T_0 + 2$ hrs$T_0 + 4$ hrs$T_0 + 8$ hrs$T_0 + 12$ hrs	
Pre-T_0	
Pre-T_0	
Pre-T_0$T_0 + 2$ hrs$T_0 + 4$ hrs$T_0 + 8$ hrs$T_0 + 12$ hrs
Treatment Groups/ Comparisons	H-1337 vs. Vehicle	H-1337 vs. Vehicle	H-1337 vs. Vehicle	H-1337 vs. Vehicle

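### Does calling the hyperemia SD both 20% of the scale range and 1 unit leave the stated power in doubt?

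*Protocol*

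**What the plan says.** Protocol 8.1 describes the outcome as "Hyperemia: Scored on a 5-point scale from 0 to 3". The grading text in Protocol section 5 agrees: "The hyperemia will be graded on a 0 to 3 scale using the photographic reference scale", with levels 0, 0.5, 1, 2 and 3. The SD follows: "Assume the SD is 20% of the scale range or 1 unit". With 20 per group, a two-sided t-test and alpha 0.05, the protocol then claims that "there is 86% power to detect a mean difference of 1 unit between pairs of groups". A conditional sentence adds a Fisher's exact calculation for a responder defined by a score of at least 3: control rate 10%, difference 46 percentage points, power 85%. The power text then generalises: "In general, with 20 subjects per group there is 86% power to detect an effect size of 1.0". The same SD wording stands in the protocol synopsis and in SAP section 4.

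On analysis, SAP 7.13 plans frequency tables and says that "the photographic assessment of ocular hyperemia will be summarized by descriptive statistics". SAP Appendix 2 lists "H-1337 vs. Vehicle" in the comparison row for hyperemia. A between-arm model is named only for IOP, in SAP 7.4: "each of the active treatment groups will be compared to the placebo group using the analysis of covariance (ANCOVA) model".

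**The concern.** The sentence offers two SDs as if they were one, and on a 0 to 3 scale they differ by a factor of 1/0.6 = 1.67. The detectable difference scales directly with the SD. At 80% power it is 0.91 unit if the SD is 1 and 0.55 unit if it is 0.6. Most steps on the scale are 1 unit wide, so those two figures would support different readings of a null result.

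Hyperemia also matters here. Safety is the primary objective, and the protocol background names hyperemia as the most frequent adverse event with rho kinase inhibitors and reports it in preclinical work with H-1337. If the assumed SD were unknown, the reader could not say what the study is able to detect on its leading expected safety signal.

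A second worry sits beside the first. Power is quoted for a t-test and a Fisher test, yet the SAP names no hyperemia test and no responder variable. That could look like a choice left open until after unmasking.

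**Working it through.** **Inputs.** From Protocol 8.1: n = 20 per group, difference 1 unit, two-sided alpha 0.05, two-group t-test, stated power 86%. From Protocol section 5: lowest grade 0, highest grade 3.

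**The label.** Range = 3 − 0 = 3. Then 0.20 × 3 = 0.6 unit, and 1/3 = 33%. For 20% to equal 1 unit the range would have to be 1/0.20 = 5. The scale has five levels, so the number of levels may have been taken for the range; the documents do not confirm this.

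**Method.** Power comes from the noncentral t distribution with df = 2 × 20 − 2 = 38 and noncentrality (difference/SD) × √(n/2).

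**The plan's own figure.** With SD = 1, noncentrality = 1 × √10 = 3.16 and power = 86.9%. This reproduces the stated 86% to within one point.

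**The other reading and its neighbours:**

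| SD (units) | Share of range | Power for a 1-unit difference |
|---|---|---|
| 1.0 | 33% | 86.9% |
| 0.8 | 27% | 97.1% |
| 0.6 | 20% | 99.9% |

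With SD = 0.6 the noncentrality is (1/0.6) × √10 = 5.27. Working backwards, the SD that gives exactly 86% is 1.01, and SDs from about 0.98 to 1.04 fall within 2 points of 86%. An SD of 0.6 is far outside that band.

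**Internal cross-check.** An effect size is difference/SD. The general statement gives 86% for an effect size of 1.0, the same power as for a 1-unit hyperemia difference. The two agree only if SD = 1 unit.

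**Detectable differences, n = 20 per group.** SD 1: 0.99 unit at 86% power and 0.91 at 80%. SD 0.6: 0.59 and 0.55.

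**Neighbouring figures.** Fisher's exact test, 10% against 10% + 46% = 56%, gives 85.5% (stated 85%). IOP, difference 4.0 mmHg and SD 3.5 mmHg, gives 94.1% (stated 94%). Both reproduce, so the error does not extend beyond the label.

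**The planned analysis.** Protocol 8.2 says continuous and ordinal measures will be summarised descriptively and allows shift tables for selected safety measures. SAP 7.13 does the same for hyperemia. The two documents agree. The Appendix 2 comparison label is identical in every column, including Day 0. On Day 0 the first dose is given only after the 12-hour IOP reading, and hyperemia is graded before IOP, so every Day 0 grade precedes treatment. A label that also applies to pre-dose data is better read as naming the groups displayed than as committing to a test.

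**The case for a change.** The strongest case for acting is that the error appears in three places across two documents, so it is not an extraction artefact. It concerns the safety measure most likely to show a signal, no source is given for the SD, and the correction would cost one sentence in each place. Power figures for tests that the SAP does not name also leave room for a choice of test and time point after unmasking.

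Part of this stands. The label is wrong wherever it appears, and the value of 1 unit is unsourced. But the claim that the assumed SD cannot be identified does not survive the arithmetic: difference, sample size, test, alpha and power are all given, and together they fix the SD at about 1.

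Hyperemia is also not the only safety measure with a between-arm power. The effect-size statement covers any continuous measure, and hyperemia is one instance of it.

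On the missing test, the protocol calls the trial small and exploratory, and both documents plan descriptive summaries. The responder calculation is conditional, so the absence of a responder variable breaks no commitment. Quoting power to convey how much information 20 per group carries is compatible with descriptive reporting. Rewriting the text around an SD of 0.6 would make matters worse, because it would contradict the stated 86% for 1 unit.

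**Conclusion.** The percentage is a clerical slip and nothing in the plan depends on it. The SD in use is 1 unit, or 33% of the 0 to 3 range, and the power statement built on it is right (86.9% against 86% stated). The number per group is set by IOP and does not move. Had 0.6 been meant, the plan would have understated its power (86% against 99.9%), so the slip cannot make the study look stronger than it is. The lack of a named hyperemia test is consistent with the descriptive analysis planned in both documents and needs no further specification in an exploratory trial.

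This rests on taking the t-test, alpha and 20 per group as written, with no allowance for dropout. It shows which SD was assumed, not that 1 unit is the SD the trial will observe; the documents give no data for that. Anyone editing these sections for another reason could drop or correct the percentage, but no stated power, planned analysis or conclusion would change.

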8.2 Statistical Methods

Continuous and ordinal measures will be summarized by descriptive statistics (n, mean, standard deviation, median, minimum and maximum values). Qualitative measures will be tabulated by counts and percentages. Selected safety measures may be summarized by the use of shift tables. Summary tables will show the data for each time point (visit and/or time of day as appropriate) and will display the observed and change (and for IOP the % change) from baseline value.

A statistical analysis plan will be prepared prior to unmasking the treatment assignments.

An analysis of results will be conducted when the database for each stage has been locked and the treatment assignments have been revealed. No within-stage interim analyses are planned.

8.3 Subject Population(s) for Analysis

Up to approximately 4 to 8 US sites will be active.

All subjects who receive IP and at least one dose will be evaluable for the safety analysis. For efficacy considerations, the primary analysis population will be the intent-to-treat (ITT) population. All subjects who receive study medication and who complete at least one on-therapy study visit will be evaluable for the ITT analyses. Subjects who receive study

medication, satisfy pre-randomization inclusion/exclusion criteria, and who complete at least one on-therapy study visit will be evaluable for a per protocol population analysis. Individual subject visits and data points that do not satisfy protocol criteria may be excluded from per protocol analyses. Evaluability will be determined prior to breaking the code for masked treatment assignment.

8.4 Significance

For superiority testing, a 2-sided test with a significance level of $p \leq 0.05$ will be used.

8.5 Accountability Procedure

It is expected that in this small trial of brief duration, the incidence of missing data will be kept to a minimum. Sites, subjects and Allysta Pharmaceuticals, Inc., or its representative will be trained in methods to encourage continued participation to maximize the completion rate and overall quality of the trial. As this is a small Phase 1/2a exploratory trial, there are no plans to impute values for missing data. With regard to the primary efficacy variable, IOP, there are steps taken in the procedure for collecting these data that minimize the likelihood of spurious data.

8.6 Deviation Reporting

Any deviations from the statistical plan enumerated in the protocol or final statistical plan will be described and justified in the clinical study report.

9 DIRECT ACCESS TO SOURCE DATA/DOCUMENTATION

Study visits will be conducted by an authorized Allysta Pharmaceuticals, Inc., representative to inspect study data, subjects' medical records, and CRFs in accordance with current US Good Clinical Practices (GCP) and the respective local, national government and international regulations and guidelines.

The investigator will permit authorized representatives of Allysta Pharmaceuticals, Inc., or its representative, the Food and Drug Administration (FDA), and the appropriate health authorities to inspect facilities and records relevant to this study.

10 DATA REVIEW AND ANALYSIS

There will be no formal external Data Monitoring Committee. The masked data will be continually monitored on an ongoing basis, according to the safety plan, as subjects are enrolled and complete the study. During the study, investigators, site personnel, and Allysta Pharmaceuticals personnel responsible for the daily conduct of the study will remain masked to the results to maintain the scientific rigor and credibility of the trial. Allysta Pharmaceuticals personnel and selected external consultants will be unmasked once data is locked. Data will then be reviewed, the safety and efficacy for each dose determined.

11 QUALITY CONTROL AND QUALITY ASSURANCE

Each investigator must adhere to the protocol as detailed in this document and agrees that any changes to the protocol must be approved by Allysta Pharmaceuticals, Inc., prior to seeking approval from the IRB/Ethics Committee. Each investigator will be responsible for enrolling only those subjects who have met protocol eligibility criteria. During study conduct, Allysta Pharmaceuticals and/or its representative will conduct periodic monitoring visits to ensure that the protocol and Good Clinical Practices (GCPs) are being followed. The monitors may review source documents to confirm that the data recorded on CRFs is accurate. The investigator and institution will allow Allysta Pharmaceuticals, Inc., monitors or its agents and appropriate regulatory authorities direct access to source documents and CRFs to perform this verification.

It is important that the investigator(s) and their relevant personnel are available during the monitoring visits and possible audits or inspections and that sufficient time is devoted to the process.

12 ETHICAL CONSIDERATIONS

This study will be conducted in accordance with current US FDA regulations, International Conference on Harmonization (ICH) guidelines, Good Clinical Practice (GCP) standards, the Declaration of Helsinki, and local ethical and legal requirements. The Principal Investigator must sign the protocol signature page to indicate acceptance of the protocol.

12.1 Informed Consent

The subject must sign the Informed Consent Document before his or her participation in the study. A copy of the Informed Consent Document must be provided to the subject or the subject's legal guardian. If applicable, it will be provided in a certified translation of the subject's first or native language. The original signed informed consent document for each participating subject shall be filed with records kept by the investigator and must be available for verification by study monitors at any time, and a copy will be given to each subject.

12.2 Institutional Review Board/Ethics Committee

This protocol, the informed consent document, relevant supporting information and all types of subject recruitment or advertisement information must be submitted to the IRB/Ethics Committee for review and must be approved before the study is initiated. Any amendments to the protocol must also be approved by the IRB/Ethics Committee prior to implementing changes in the study. The investigator is responsible for keeping the IRB/Ethics Committee apprised of the progress of the study, any SAEs, and any changes made to the protocol according to the requirements of the site's IRB.

12.3 Confidentiality

The information obtained during the conduct of this clinical study is confidential, and disclosure to third parties other than those noted below is strictly prohibited. Information obtained during the conduct of this study will be used by Allysta Pharmaceuticals, Inc., in connection with the development of the IP. The study investigator is obliged to provide Allysta Pharmaceuticals, Inc., or designee with complete test results and all data developed in this study. This information may be disclosed to other physicians who are conducting similar studies and to the FDA as deemed necessary by Allysta Pharmaceuticals, Inc. Subject-specific information may be provided to other appropriate medical personnel only with the subject's permission.

12.4 Early Sponsor Discontinuation of the Trial

All clinical investigational data will be reviewed by the Medical Monitor on a regular basis. Reports of all data will be made available to the appropriate IRB/Ethics Committee and to the FDA. The clinical investigation may be suspended if the Medical Monitor, upon review and evaluation of the clinical data, finds the severity or incidence of single or total complications unacceptable for continuation of the investigation.

13 DATA HANDLING AND RECORD KEEPING

The investigator must retain all study records according to ICH guidelines and according to the record retention policies of the country where the study is being conducted. FDA requires that records are retained for at least 2 years after a marketing application is approved for the drug, or if an application is not approved, until 2 years after FDA has been notified of the discontinuation of the investigational use of the drug (21CFR312.57).

A _{max}	Peak Concentration
AMD	Age-related Macular Degeneration
ANCOVA	Analysis of Covariance
AP	Alkaline Phosphatase
AST	Aspartate Aminotransferase
AUC	Area Under the Curve
BAK	Benzalkonium Chloride
BCVA	Best Corrected Visual Acuity
BID	Twice Daily
BP	Blood Pressure
BUN	Blood Urea Nitrogen
CFB	Change From Baseline
CPK	Creatine Phosphokinase
ECG	Electrocardiogram
ET	Early Termination
ETDRS	Early Treatment Diabetic Retinopathy Study
GFR	Glomerular Filtration Rate
GGT	Gamma-Glutamyl Transferase
Hg	Mercury
HIV	Human Immunodeficiency Virus
Hrs	Hours
IC	Informed Consent Document
IND	Investigational New Drug
IOP	Intraocular Pressure
IP	Investigational Product
IWRS	Interactive Web Response System
LASIK	Laser-Assisted In Situ Keratomileusis
LDH	Lactate Dehydrogenase
MedDRA	Medical Dictionary for Regulatory Activities
Mm	Millimeter
OTC	Over The Counter
OU	Both Eyes
PAS	Peripheral Anterior Synechiae
PK	Pharmacokinetic

POAG	Primary Open Angle Glaucoma
PRK	Photorefractive Keratectomy
PT	Preferred Term
RBC	Red Blood Cell
RGC	Retinal Ganglion Cells
ROCK	Rho Kinase
SAE	Serious Adverse Event
SAP	Statistical Analysis Plan
SLT	Selective Laser Trabeculoplasty
TEAE	Treatment Emergent Adverse Event
TM	Trabecular Meshwork
T _{max}	Time to Peak Concentration
US	United States
VF	Visual Fields
WBC	White Blood Cell

This is version 1 of the statistical analysis plan (SAP) for study ALY337-201. If revisions are needed, the document will be amended. The SAP should be finalized prior to the database lock and final unmasking. All deviations from the analyses described in the final SAP will be noted in the clinical study report (CSR).

